10.3.4. Reporting of SAEs

SAE Reporting via Paper CRF

- Facsimile transmission of the SAE Report is the preferred method to transmit this information to the sponsor or designee.
- Initial notification via telephone does not replace the need for the investigator to complete and sign the SAE Report within the designated reporting time frames.

- Contacts for SAE reporting can be found in the SAE Report.

10.4. Appendix 4: Contraceptive Guidance and Collection of Pregnancy Information

10.4.1. Women

Only women of non-childbearing potential may participate in this study.

Definitions:

Woman of Childbearing Potential

A woman is considered fertile following menarche and until becoming postmenopausal unless permanently sterile (see below).

If fertility is unclear (e.g., amenorrhea in adolescents or athletes) and a menstrual cycle cannot be confirmed before first dose of study intervention, additional evaluation should be considered.

Woman Not of Childbearing Potential

Women in the following categories are not considered woman of childbearing potential

1. Premenarchal

2. Premenopausal female with 1 of the following:

- Documented hysterectomy
- Documented bilateral salpingectomy
- Documented bilateral oophorectomy

For individuals with permanent infertility due to an alternate medical cause other than the above, (e.g., mullerian agenesis, androgen insensitivity), investigator discretion should be applied to determining study entry.

Note: Documentation can come from the site personnel's: review of the participant's medical records, medical examination, or medical history interview.

3. Postmenopausal female is defined as, women with

- 12 months of amenorrhea for women >55 years, with no need for follicle-stimulating hormone (FSH)
- 12 months of amenorrhea for women >40 years with FSH ≥ 40 mIU/mL and no other medical condition such as anorexia nervosa and not taking medications during the amenorrhea (e.g. oral contraceptives, hormones, gonadotropin-releasing hormone, anti-estrogens, selective estrogen receptor modulators, or chemotherapy that induced amenorrhea)

10.4.2. Men

Men, regardless of their fertility status, must agree to either remain abstinent (if this is their preferred and usual lifestyle) or use condoms as well as 1 additional highly effective method of contraception (less than 1% failure rate) or effective method of contraception with nonpregnant women of childbearing potential partners for the duration of the study and until their plasma concentrations are below the level that could result in a relevant potential exposure to a possible fetus, predicted to be 140 days after the last dose.

Men with pregnant partners should use condoms during intercourse for the duration of the study and until the end of estimated relevant potential exposure to the fetus, predicted to be 140 days after the last dose.

Acceptable Methods of Contraception for Female Partners of Male Participants

Highly effective methods of contraception (less than 1% failure rate) comprise, but are not limited to

- combination oral contraceptives
- implanted contraceptives, or
- intrauterine devices.

Effective methods of contraception comprise but are not limited to diaphragms with spermicide or cervical sponges.

Men and their partners may choose to use a double-barrier method of contraception that must include use of a spermicide.

10.4.3. Collection of Pregnancy Information

Male participants with partners who become pregnant

The investigator will attempt to collect pregnancy information on any male participant's female partner who becomes pregnant while the male participant is in this study. This applies only to male participants who receive study intervention.

After obtaining the necessary signed informed consent from the pregnant female partner directly, the investigator will record pregnancy information on the appropriate form and submit it to the sponsor within 24 hours of learning of the partner's pregnancy.

The female partner will also be followed up to determine the outcome of the pregnancy. Information on the status of the mother and child will be forwarded to the sponsor. Generally, the follow-up will be no longer than 6 to 8 weeks following the estimated delivery date. Any termination of the pregnancy will be reported including fetal status (presence or absence of anomalies) and indication for the procedure.

Female participants who become pregnant

The investigator will collect pregnancy information on any female participant who becomes pregnant while participating in this study. The initial information will be recorded on the appropriate form and submitted to the sponsor within 24 hours of learning of a participant's pregnancy.

The participant will be followed up to determine the outcome of the pregnancy. The investigator will collect follow-up information on the participant and the neonate and the information will be forwarded to the sponsor. Generally, follow-up will not be required for longer than 6 to 8 weeks beyond the estimated delivery date. Any termination of pregnancy will be reported, including fetal status (presence or absence of anomalies) or indication for the procedure.

While pregnancy itself is not considered to be an AE or SAE, any pregnancy complication or elective termination of a pregnancy for medical reasons will be reported as an AE or SAE.

A spontaneous abortion (occurring at <20 weeks gestational age) or still birth (occurring at >20 weeks gestational age) is always considered to be an SAE and will be reported as such.

Any poststudy pregnancy-related SAE considered reasonably related to the study intervention by the investigator will be reported to the sponsor as described in Section 8.3.4. While the investigator is not obligated to actively seek this information in former study participants, he or she may learn of an SAE through spontaneous reporting.

10.5. Appendix 5: Genetics

Sample collection information is found in Appendix 2, Section 10.2 (Clinical Laboratory Tests).

Genetic variation may impact a participant's response to study intervention, susceptibility to, and severity and progression of disease. Variable response to study intervention may be due to genetic determinants that impact drug absorption, distribution, metabolism, and excretion; mechanism of action of the drug; disease etiology; and/or molecular subtype of the disease being treated. Therefore, where local regulations and IRB/IEC allow, a blood sample will be collected for DNA analysis from consenting participants.

DNA samples may be used for research related to SARS-CoV-2 and related diseases. They may also be used to develop tests/assays including diagnostic tests related to LY3832479 or SARS-CoV-2. Genetic research may consist of the analysis of 1 or more candidate genes or the analysis of genetic markers throughout the genome as appropriate.

The samples may be analyzed as part of a multistudy assessment of genetic factors involved in the response to LY3832479 or study interventions of this class to understand study disease or related conditions.

The results of genetic analyses may be reported in the clinical study report or in a separate study summary.

The sponsor will store the DNA samples in a secure storage space with adequate measures to protect confidentiality.

The samples will be retained at a facility selected by the sponsor or its designee while research on SARS-CoV-2 continues but no longer than 15 years or other period as per local requirements.

10.6. Appendix 6: Liver Safety: Suggested Actions and Follow-Up Assessments

Hepatic Evaluation Testing

See Section 8.2.4 for guidance on appropriate test selection.

Testing will be performed locally.

Hematology	Clinical Chemistry
Hemoglobin	Total bilirubin
Hematocrit	Direct bilirubin
Erythrocytes (RBCs - red blood cells)	Alkaline phosphatase (ALP)
Leukocytes (WBCs - white blood cells)	Alanine aminotransferase (ALT)
Differential:	Aspartate aminotransferase (AST)
Neutrophils, segmented	Gamma-glutamyl transferase (GGT)
Lymphocytes	Creatine kinase (CK)
Monocytes	Other Chemistry
Basophils	Acetaminophen
Eosinophils	Acetaminophen protein adducts
Platelets	Alkaline phosphatase isoenzymes
Cell morphology (RBC and WBC)	Ceruloplasmin
	Copper
Coagulation	Ethyl alcohol (EtOH)
Prothrombin time, INR (PT-INR)	Haptoglobin
	Immunoglobulin IgA (quantitative)
Serology	
Hepatitis A virus (HAV) testing:	Immunoglobulin IgG (quantitative)
HAV total antibody	Immunoglobulin IgM (quantitative)
HAV IgM antibody	Phosphatidylethanol (PEth)
Hepatitis B virus (HBV) testing:	Urine Chemistry
Hepatitis B surface antigen (HBsAg)	Drug screen
Hepatitis B surface antibody (anti-HBs)	Ethyl glucuronide (EtG)
Hepatitis B core total antibody (anti-HBc)	Other Serology
Hepatitis B core IgM antibody	Anti-nuclear antibody (ANA)
Hepatitis B core IgG antibody	Anti-smooth muscle antibody (ASMA) ^a
HBV DNA ^c	Anti-actin antibody ^b
Hepatitis C virus (HCV) testing:	Epstein-Barr virus (EBV) testing:
HCV antibody	EBV antibody

HCV RNA ^c	EBV DNA ^c
Hepatitis D virus (HDV) testing:	Cytomegalovirus (CMV) testing:
HDV antibody	CMV antibody
Hepatitis E virus (HEV) testing:	CMV DNA ^c
HEV IgG antibody	Herpes simplex virus (HSV) testing:
HEV IgM antibody	HSV (Type 1 and 2) antibody
HEV RNA ^c	HSV (Type 1 and 2) DNA ^c
Microbiology	Liver kidney microsomal type 1 (LKM-1) antibody
Culture:	
Blood	
Urine	

^a Not required if anti-actin antibody is tested.

^b Not required if anti-smooth muscle antibody (ASMA) is tested.

^c Reflex/confirmation dependent on regulatory requirements, testing availability, or both.

10.7. Appendix 7: Recommended Laboratory Testing for Hypersensitivity Events

Laboratory assessments should be performed if the participant experiences generalized urticaria or if anaphylaxis is suspected.

- Collect sample after the participant has been stabilized, and within 1 to 2 hours of the event; however, samples may be obtained as late as 12 hours after the event as analytes can remain altered for an extended period of time. Record the time at which the sample was collected.
- Obtain a follow-up sample after approximately 4 weeks.

Clinical Laboratory Tests for Hypersensitivity Events

Hypersensitivity Tests	Notes
	Selected test may be obtained in the event of anaphylaxis or systemic allergic/hypersensitivity reactions.
LY3832479 antidrug antibodies (immunogenicity/ADAs)	Assayed by Lilly-designated laboratory. Results will not be provided to the study sites.
LY3832479 concentrations (PK)	Assayed by Lilly-designated laboratory. Results will not be provided to the study sites.
Tryptase	Assayed by Lilly-designated laboratory. Results will not be provided to the study sites. The study site should attempt to obtain a tryptase sample within 2 hours of the event. If more than 12 hours have passed since the event, no tryptase sample should be obtained. If the tryptase sample is obtained between 2 and 12 hours, or is not obtained, the site should collect a urine sample for N-methylhistamine testing. Collect the first void urine following the event. Collect a follow-up urine sample after approximately 4 weeks.
N-methylhistamine	Assayed by Lilly-designated laboratory. Results will not be provided to the study sites.
Drug-specific IgE	Will be performed if a validated assay is available. Assayed by Lilly-designated laboratory. Results will not be provided to the study sites.
Basophil activation test	Will be performed if a validated assay is available. Assayed by Lilly-designated laboratory. Results will not be provided to the study sites. NOTE: The basophil activation test is an in vitro cell-based assay that only requires a serum sample. It is a surrogate assay for drug specific IgE but is not specific for IgE.
Complement (C3, C3a and C5a)	Assayed by Lilly-designated laboratory. Results will not be provided to the study sites.
Cytokine panel	Assayed by Lilly-designated laboratory. Results will not be provided to the study sites.

Abbreviations: IgE = immunoglobulin E; PK = pharmacokinetics.

10.8. Appendix 8: Abbreviations

Term	Definition
ACE2	angiotensin-converting enzyme 2
ADA	antidrug antibody
ADE	antibody-dependent enhancement
AE	adverse event
ALP	alkaline phosphatase
ALT	alanine aminotransferase
AST	aspartate aminotransferase
blinding	A double-blind study is 1 in which neither the participant nor any of the investigator or sponsor personnel who are involved in the treatment or clinical evaluation of the participants are aware of the treatment received.
BMI	body mass index
BP	blood pressure
CFR	Code of Federal Regulations
CK	creatinine kinase
CMV	cytomegalovirus
CT	computed tomography
Complaint	A complaint is any written, electronic, or oral communication that alleges deficiencies related to the identity, quality, purity, durability, reliability, safety or effectiveness, or performance of a drug or drug delivery system.
compliance	Adherence to all study-related, good clinical practice (GCP), and applicable regulatory requirements.
COVID-19	coronavirus disease 2019
CRP	clinical research physician: Individual responsible for the medical conduct of the study. Responsibilities of the CRP may be performed by a physician, clinical research scientist, global safety physician, or other medical officer.
CRU	clinical research unit
D. Bil	direct bilirubin
EBV	Epstein-Barr virus
ECG	electrocardiogram

eCRF	electronic case report form
EDC	electronic data capture
enroll	The act of assigning a participant to a treatment. Participants who are enrolled in the study are those who have been assigned to a treatment.
enter	Participants entered into a study are those who sign the informed consent form directly or through their legally acceptable representatives.
ERCP	endoscopic retrograde cholangiopancreatography
FSH	follicle-stimulating hormone
GCP	good clinical practice
GGT	gamma-glutamyltransferase
GLP	good laboratory practice
HCV	hepatitis C virus
HDV	hepatitis D virus
HIV	human immunodeficiency virus
IB	Investigator's Brochure
ICF	informed consent form
ICH	International Council for Harmonisation
IEC	independent ethics committee
Ig	immunoglobulin
informed consent	A process by which a participant voluntarily confirms his or her willingness to participate in a particular study, after having been informed of all aspects of the study that are relevant to the participant's decision to participate. Informed consent is documented by means of a written, signed, and dated informed consent form.

2. ABBREVIATIONS

Abbreviations pertain to the Statistical Analysis Plan (SAP) only (not the tables, figures and listings [TFLs]).

AE	Adverse event
ALP	Alkaline phosphatase
ALT	Alanine aminotransferase
AST	Aspartate aminotransferase
AUC	Area under the concentration versus time curve
AUC(0-∞)	Area under the concentration versus time curve from time zero to infinity
AUC(0-t _{last})	Area under the concentration versus time curve from time zero to time t, where t is the last time point with a measurable concentration
%AUC(t _{last} -∞)	Percentage of AUC(0-∞) extrapolated
BQL	Below the lower limit of quantification
CL	Total body clearance of drug calculated
C _{max}	Maximum observed drug concentration
CRF	Case Report Form
CRU	Clinical Research Unit
CSR	Clinical Study Report
CV	Coefficient of variation
DAIDS	Division of Allergy and Infectious Diseases
ECG	Electrocardiogram
ICF	Informed consent form
ICH	International Conference on Harmonisation
IV	Intravenous
MedDRA	Medical Dictionary for Regulatory Activities
MRE	Magnetic resonance elastography
PK	Pharmacokinetic
SAP	Statistical Analysis Plan
SARS-CoV-2	Severe acute respiratory syndrome coronavirus 2
SD	Standard deviation
TFLs	Tables, Figures, and Listings

$t_{1/2}$	Half-life associated with the terminal rate constant (λ_z) in non-compartmental analysis
TBL	Total bilirubin
t_{last}	Time of the last observed drug concentration
t_{max}	Time of maximum observed drug concentration
ULN	Upper limit of normal
V_{ss}	Volume of distribution at steady state
V_z	Volume of distribution during the terminal phase
WHO	World Health Organization

3. INTRODUCTION

This SAP has been developed after review of the Clinical Study Protocol (final version dated 03 June 2020) and Protocol Amendment (c) (final version dated 15 July 2020).

This SAP describes the planned analysis of the safety, tolerability, and pharmacokinetic (PK) data from this study. A detailed description of the planned TFLs to be presented in the clinical study report (CSR) is provided in the accompanying TFL shell document.

The intent of this document is to provide guidance for the statistical and PK analyses of data. In general, the analyses are based on information from the protocol, unless they have been modified by agreement with Eli Lilly and Company. A limited amount of information concerning this study (e.g., objectives, study design) is given to help the reader's interpretation. When the SAP and TFL shells are agreed upon and finalized, they will serve as the template for this study's CSR.

This SAP supersedes the statistical considerations identified in the protocol; where considerations are substantially different, they will be so identified. If additional analyses are required to supplement the planned analyses described in this SAP, they may be performed and will be identified in the CSR. Any substantial deviations from this SAP will be agreed upon with Eli Lilly and Company and identified in the CSR. Any minor deviations from the TFLs may not be documented in the CSR.

This SAP is written with consideration of the recommendations outlined in the International Conference on Harmonisation (ICH) E9 Guideline entitled Guidance for Industry: Statistical Principles for Clinical Trials¹ and the ICH E3 Guideline entitled Guidance for Industry: Structure and Content of Clinical Study Reports².

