1.1. Synopsis

Protocol Title: A Phase 1, Randomized, Placebo-Controlled Study to Evaluate the Tolerability, Safety, Pharmacokinetics, and Immunogenicity of LY3832479 Given as a Single Intravenous Dose in Healthy Participants

Short Title: A Phase 1, Randomized, Placebo-Controlled Study to Evaluate LY3832479 in Healthy Participants

Rationale:

Lilly is developing LY3832479 for the treatment and prevention of coronavirus disease 2019 (COVID-19). Study J2Z-MC-PGAA (PGAA) will investigate the safety, tolerability, and pharmacokinetics of LY3832479 when administered as a single intravenous dose to healthy participants.

Objectives and Endpoints

Objectives	Endpoints
Primary	

To investigate the safety and tolerability of a single dose of LY3832479 in healthy participants	
Serious and nonserious adverse events, laboratory measures of safety, ECG, and vital signs
Secondary	
AUC, Cmax

Abbreviations: AUC = area under the concentration versus time curve; Cmax = maximum observed drug concentration; ECG = electrocardiogram; IV = intravenous.

Overall Design

Study PGAA is a Phase 1, randomized, placebo-controlled study of LY3832479 administered to healthy participants.

The study will comprise up to 3 cohorts, each with an intended number of participants as follows:

Cohorts 1 and 2

At least 9 participants:

- 7 randomized to LY3832479 and
- 2 randomized to placebo.

Cohort 3

At least 8 participants:

- 6 randomized to LY3832479 and
- 2 randomized to placebo.

Participants will be initially monitored for safety within the study site where they will be admitted on Day -1, dosed on Day 1, discharged on Day 4, and subsequently monitored on an outpatient basis until the last follow-up visit.

[figure not shown]
Disclosure Statement: This is a sequential, single-ascending dose study with up to 3 cohorts that is participant and investigator blinded.

Number of Participants:

A maximum of 30 participants will be enrolled to study intervention such that approximately 8 participants have sufficient evaluable data in each of the 3 cohorts.

Intervention Groups and Duration:

Single-dose study with an estimated duration for each participant of up to 16 weeks from screening through follow-up.

Data Monitoring Committee: No**1.2. Schema**

Abbreviations: LY = LY3832479; PBO = placebo; PK = pharmacokinetics.

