6. TREATMENTS

The following is a list of the study treatment abbreviations that will be used in the TFLs.

Cohort	Study Treatment Name	Treatment order in TFL
All	Pooled placebo IV	1
1	700 mg LY3832479 IV	2
2	2800 mg LY3832479 IV	3
3	7000 mg LY3832479 IV	4

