9. STATISTICAL METHODOLOGY

9.1 General

Data listings will be provided for all data that are databased. Summary statistics and statistical analysis will only be presented for data where detailed in this SAP. For continuous data, summary statistics will include the arithmetic mean, arithmetic standard deviation (SD), median, minimum, maximum, and N; for log-normal data (e.g. the PK parameters: AUCs and C_{max}) the geometric mean and geometric coefficient of variation (CV%) will also be presented. For categorical data, frequency count and percentages will be presented. Data listings will be provided for all subjects up to the point of withdrawal, with any subjects excluded from the relevant population highlighted. Summary statistics and statistical analyses will generally only be performed for subjects included in the relevant analysis population. For the calculation of summary statistics and statistical analysis, unrounded data will be used.

Mean change from baseline is the mean of all individual subjects' change from baseline values. Each individual change from baseline will be calculated by subtracting the individual subject's baseline value from the value at the timepoint. The individual subject's change from baseline values will be used to calculate the mean change from baseline using a SAS procedure such as Proc Univariate.

Data analysis will be performed using SAS® Version 9.4 or greater.

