9.4.10 Other assessments

All other safety assessments not detailed in this section will be listed but not summarized or statistically analyzed.

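### The SAP has no immunogenicity analysis, so read literally it drops the exploratory ADA summaries in Protocol 9.4.4 without declaring this in SAP 11

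*SAP*

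**What the plan says.** **Protocol.** The study title announces a "Study to Evaluate the Tolerability, Safety, Pharmacokinetics, and Immunogenicity of LY3832479 Given as a Single Intravenous Dose in Healthy Participants". Section 9.4.4 makes three firm commitments:
- the number and percentage of participants with preexisting ADA;
- the number and percentage with treatment-emergent ADA (TE ADA+), under a 2-fold titer rule if baseline is negative and a 4-fold rule if baseline is positive;
- the distribution of maximum titers among TE ADA+ participants.

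Two further items, neutralizing antibodies and the relation of ADA to PK or safety, are worded as optional. Section 9.4 says the SAP will give a more detailed account of the analyses in that section. It also says that changes to the analysis methods, with their justification, will appear in the SAP and the clinical study report (CSR).

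**SAP.** Section 3 states: "This SAP describes the planned analysis of the safety, tolerability, and pharmacokinetic (PK) data from this study". It then says "In general, the analyses are based on information from the protocol", unless modified by agreement with the sponsor, but also "This SAP supersedes the statistical considerations identified in the protocol; where considerations are substantially different, they will be so identified". Section 9.1 adds: "Summary statistics and statistical analysis will only be presented for data where detailed in this SAP". Section 9.4.10 closes the safety methods with: "All other safety assessments not detailed in this section will be listed but not summarized or statistically analyzed". Section 11 declares that nothing changed from the protocol's analyses. The contents list, abbreviations, objectives, populations and methods do not mention immunogenicity, ADA, titers or neutralizing antibodies.

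**The concern.** A gap in a SAP is often harmless, because the protocol text stands behind it. Here the SAP's own rules give its silence an effect: it supersedes the protocol's statistical considerations, and it summarizes only what it details. A programmer who followed it would have no instruction to produce the ADA tables and a general rule against producing them. A reader who turned to SAP 11 would be told that nothing had changed.

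At stake are the pre-specified summaries of a topic named in the study title, for which the protocol draws five samples per participant (Protocol 10.2.1). If the tables were later added to the CSR, they would look like supplementary analyses, although the protocol had committed to them from the start.

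**Working it through.** The question is textual and the plan states no figure to reproduce. The check sets the commitments against the SAP.

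**1. Commitments and counterparts**

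| Protocol 9.4.4 output | Status | SAP counterpart |
|---|---|---|
| Preexisting ADA, n and % | firm | none |
| TE ADA+, n and % | firm | none |
| Maximum-titer distribution in TE ADA+ | firm | none |
| Neutralizing antibody frequency | optional | none (not counted) |
| ADA versus PK or safety | optional | none (not counted) |

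Firm outputs covered: 0 of 3. The first two share one protocol sentence, so counted by sentence it is 0 of 2.

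**2. Scope.** The title names tolerability, safety, pharmacokinetics and immunogenicity, which is 4 topics. The SAP 3 scope sentence names safety, tolerability and PK, which is 3. Immunogenicity is the one missing.

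**3. Could another SAP rule bring the summaries back?**
- As a separate data type, ADA falls under SAP 9.1: not detailed, therefore not summarized.
- As a safety assessment, ADA falls under SAP 9.4.10: listed only.
- SAP 9.1 also provides listings of all databased data, so ADA listings can survive. The summaries cannot.

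**4. Consistency with SAP 11.** Either the ADA summaries are still planned, and SAP 9.1 wrongly excludes them, or they are not planned, and SAP 11 is wrong. The SAP sections cannot all stand with Protocol 9.4.4.

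**5. What is already settled, and what is not.** The TE ADA+ rule is fixed in Protocol 9.4.4. SAP 6 supplies the table columns, introduced by "The following is a list of the study treatment abbreviations that will be used in the TFLs". At the minimum planned cohort sizes (the documents say at least 9, 9 and 8, with a maximum of 30 participants), these are:
- pooled placebo: 2 + 2 + 2 = 6
- 700 mg: 7
- 2800 mg: 7
- 7000 mg: 6
- total: 6 + 7 + 7 + 6 = 26

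The denominator is not settled. The Safety population in SAP 8 would include all 26 if all are dosed. The SAP's Pharmacokinetic population is limited to LY3832479 recipients with multiple evaluable samples, so it has at most 7 + 7 + 6 = 20 and would empty the placebo column. In columns this small one participant is 1/7 = 14.3% or 1/6 = 16.7%, so the choice would show in the percentages.

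**The case against.** **Scope.** The strongest counter-argument is that SAP 3 confines the document to safety, tolerability and PK. Its precedence sentence could then be read within that scope, leaving Protocol 9.4.4 in force for ADA and SAP 11 true. The general statement that analyses follow the protocol supports this reading. It fails on SAP 9.1, which limits summaries to data the SAP itself details and makes no exception for data outside its scope. Nor is SAP 11 good evidence that nothing was meant to change. Protocol 9.4.2 has ECG parameters listed and summarized, SAP 9.4.5 says ECGs will not be presented, and SAP 11 does not mention that either.

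**The protocol's own inconsistency.** Immunogenicity is in the title and in 9.4.4 but not in the objectives tables of Protocol 1.1 and 3. SAP 4 mirrors those tables and covers both listed objectives. This stands: part of the mismatch starts in the protocol, and the count of 3 of 4 refers to title topics, not to stated objectives. It does not remove the firm commitments in 9.4.4.

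**Mitigation.** Listings would remain if the data are databased, counts could be taken from them in a study this small, and SAP 3 allows supplementary analyses identified in the CSR. SAP 3 also says: "A detailed description of the planned TFLs to be presented in the clinical study report (CSR) is provided in the accompanying TFL shell document". Those shells may well contain ADA tables. All this lowers the practical consequence, but none of it pre-specifies the analysis in the SAP or reconciles SAP 9.1, 9.4.10 and 11 with the protocol.

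**Denominator.** SAP 8 assigns no population explicitly to any endpoint, so the gap is not unique to ADA, and the Safety population is a natural candidate. That is fair, but for safety and PK the population names make the intended use plain. For ADA no population name does so.

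**Conclusion.** The concern holds. Read literally, the SAP omits all three firm immunogenicity outputs of Protocol 9.4.4 and does not declare the omission. The size is modest: the analysis is exploratory, no primary or secondary result changes, and the treatment-emergent rule itself is not in doubt. It should be corrected, but it does not threaten the study's main conclusions.

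Confidence is high that the text is absent and that the sections conflict. Whether any table will actually be missing from the CSR cannot be judged without the shells. The conclusion assumes that the unavailable SAP pages contain no immunogenicity section; the SAP's contents list shows none.

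**What to change.** Add a short immunogenicity section to the SAP that carries over the Protocol 9.4.4 definitions and its three firm outputs. Present them by the SAP 6 treatment groups, with the analysis population and denominator stated, and add immunogenicity to the scope sentence in SAP 3. Neutralizing antibody tables and ADA flags on PK listings can remain optional.

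If the sponsor does not intend these summaries in this report, SAP 11 should instead declare and justify the departure and say where ADA will be reported.

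The cost is one section and about two tables, or one statement in SAP 11. No new samples or data are needed.
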